Secondary endpoints will be serum markers of ovulation (estradiol [E₂], progesterone [P], follicle stimulating hormone [FSH], and luteinizing hormone [LH]), as well as evidence of ovulation on cervical mucus exam and transvaginal ultrasound (presence and subsequent disappearance of a dominant follicle >15 mm diameter)[19]. Blood for hormone assays will be drawn at the Bayview CRU at the same time as samples for ENG and EFV. During these visits participants will also undergo a pelvic exam for cervical mucus assessment, and a pelvic ultrasound to look for ovarian follicular activity. Monitoring throughout the study will allow us to compare ovarian activity across time points through both ultrasound visualization and ovarian hormone testing (E₂ and P). Changes in cervical mucus quality secondary to the progestin activity of ENG provide secondary contraceptive effects that may be maintained even if ovulation occurs. Continued monitoring for several weeks after cessation of EFV will allow us to follow subjects for the equivalent of a normal menstrual cycle, to ascertain whether either contraceptive effect (ovulation suppression or cervical mucus quality) was altered. Urine pregnancy tests may be repeated throughout the duration of the study as needed.

Ultrasounds and venipuncture for LH, FSH, E₂ and P levels will occur in the CRU. A total of 20 mL of venous blood will be collected for each outpatient visit. FSH, LH, E₂, and P assays will be performed by the CRU at JHU. FSH and LH will be measured using the automated immunoradiometric assay (IRMA) system. Assay sensitivity of LH assays is 0.07 mIU/ml; assay sensitivity of FSH assays is 0.2 mIU/ml. P will be measured using an automated immulite chemiluminescent assay system. Assay sensitivity of the P assay is 0.05 ng/ml. E₂ will be measured via an ultra-sensitive competitive binding radioimmunoassay with sensitivity of 2.2 pg/ml. The EFV assay will be performed through the Johns Hopkins Hospital Clinical Pharmacology Analytical Lab, and will be measured via LC-MS/MS assay with a lower limit of quantification of 0.5 ng/ml.

An assay for ENG is not commercially available, but the Irving Institute for Clinical and Translational Research at the Columbia University Medical Center in New York has developed a validated assay. ENG concentrations will be measured by LC-MS/MS, and the assay has a lower limit of quantification of 50 pg/ml.

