Transvaginal ultrasound (TVUS) will be performed using high-resolution machines (Sonosite Edge, SonoSite, Inc., Bothell, WA) in our clinic to monitor follicular development. Follicular diameter will be calculated by averaging the mean of the length and width in both the sagittal and transverse plane. Follicles measuring ≥ 10 mm will be considered dominant preovulatory follicles, and only follicles measuring ≥ 10 mm will be recorded[20]. Ovulation will be defined as the disappearance of a follicle ≥ 15 mm in diameter that was observed the visit before. We will collect cervical mucus using an endocervical aspirator, and evaluate the sample for consistency, ferning, Spinnbarkeit, and cellularity. Each variable will be scored on a 0 to 3 point scale according to WHO guidelines. A total score of 9 to 12 will indicate mucus conditions favorable to sperm penetration[21].

Recruitment: Subjects will be recruited from the general gynecology office in JHOC and practices affiliated with JHBMC. We will recruit patients known to be using Nexplanon®/Implanon®. Written notices advertising the study will be placed in the gynecology offices as well as in other affiliated primary care offices. We will also place advertising notices throughout Johns Hopkins institutions including the School of Nursing and the School of Public Health.

b. Study duration and number of study visits required of research participants.

Date: January 5th, 2017

Principal Investigator: [name], MPH

Application Number: NA_00087585

We anticipate that the study will take 12 months to complete. Participants will be enrolled for a total of 6 weeks (2 weeks taking EFV, and 4 weeks additional follow-up), during which time they will complete 14 visits including a screening visit. After enrollment, visits will occur twice weekly.

c. Blinding, including justification for blinding or not blinding the trial, if applicable.

Not applicable in this pilot pharmacokinetic study

d. Justification of why participants will not receive routine care or will have current therapy stopped.

Not applicable.

e. Justification for inclusion of a placebo or non-treatment group.

Not applicable.

f. Definition of treatment failure or participant removal criteria.

Treatment failure is not applicable to this study as efavirenz is being given to healthy volunteers and not part of an HIV treatment regimen. A participant will be removed from the study under the following circumstances:

- She misses more than three study visits

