- She becomes pregnant
- She experiences a serious adverse event
- She requests to stop the study

g. Description of what happens to participants receiving therapy when study ends or if a participant's participation in the study ends prematurely.

If a participant leaves the study prior to its completion, there will be no effect on her general medical care. At the conclusion of the study, participants will not receive any additional study medications and will return to their routine care providers for ongoing care as needed.

5. Inclusion/Exclusion Criteria

Inclusion Criteria:

- Healthy women aged 18-40 years who have a Nexplanon®/Implanon® in place that is palpable on exam, had the device placed between 12 and 24 months prior to enrollment, and can provide documentation of when the implant was placed
- Able to speak and read English
- Documented HIV-negative status within 30 days of enrollment
- BMI between 18.5 and 29.9 kg/m²
- Willingness to take a two-week course of reduced-dose efavirenz
- Willingness to comply with study visit schedule (as described below), including blood sampling, transvaginal ultrasounds, and cervical mucus assessment
- Negative urine hCG pregnancy test at study entry
- Normal laboratory values within 30 days of study entry, as specified below:
 - o White blood cell count ≥ 4500 and ≤ 11000 cells/mm³
 - o Platelet count $\geq 100,000$ platelets/mm³

Date: January 5th, 2017

Principal Investigator: [name], MPH

Application Number: NA_00087585

- Hemoglobin \geq 8.0 g/dL
 - International normalized ratio (INR) \leq 1.8
 - Aspartate transaminase (SGOT) and alanine aminotransferase (SGPT) \leq 3 times the upper limit of normal (ULN) (upper limit of normal)
 - Creatinine \leq 1.5 x ULN
 - Serum amylase \leq 1.5 x ULN
 - Total bilirubin \leq 2.0 x ULN
- Agree to use an additional reliable method of contraception while participating in the study.
Acceptable methods include:
 - Abstinence
 - Condoms (male or female) with or without spermicide
 - Pre-existing sterilization of subject or her male partner
- Willingness to abstain from alcohol consumption during the study period
- Willingness to abstain from any grapefruit product or supplement for the duration of the study.

Exclusion Criteria:

- Breastfeeding
- Hypersensitivity to efavirenz
- History of seizure disorder
- History of significant psychiatric illness
- Initiated, discontinued, or changed doses of drugs that are CYP3A4 inducers or inhibitors within 30 days of study entry.

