EFV was chosen for this study because it is the backbone of one of the preferred antiretroviral regimens recommended by the NIH[24]. As such, it is commonly taken by women of reproductive age. There is some concern that EFV increases the risk of neural-tube defects when exposure occurs during the first 5-6 weeks of pregnancy[21]. For this reason, it is particularly important to avoid unintended pregnancy in women taking EFV. Determining whether the ENG implant retains its high level of contraceptive efficacy in women taking EFV is important so that HIV-positive women and their healthcare providers can make the most informed decisions regarding antiretroviral regimens and contraception.

The dose of EFV that is used in clinical practice is 600 mg given orally once per day, typically at bedtime, and it is generally well tolerated[25]. Recent data suggest that a lower daily dose of EFV (400 mg) is as effective as the standard 600 mg dose in suppressing HIV, with lower incidence of drug-related side effects. As the criteria for starting ART continue to broaden, there is considerable concern about the costs of providing treatment to more individuals, and reducing the accepted dose of EFV is one strategy to make ART available to as many people as possible[26].

Certain drugs are contraindicated or not recommended for use with EFV, including ergot derivatives, benzodiazepines, calcium channel blockers, cisapride, pimozide, and St. John's wort. Women taking these drugs will be excluded from the study due to potential adverse drug interactions. While the 400 mg daily dose of EFV has been associated with a lower incidence of drug-related adverse events, participants will be informed of potential adverse reactions to EFV prior to enrolling in the study, and will be counseled regarding when and how to inform study personnel of any potential adverse reactions. The adverse reactions that have been identified in studies comparing EFV-based antiretroviral regimens to control regimens include:

- Psychiatric symptoms: depression (19% with EFV-based regimen vs. 16% with control), anxiety (13% vs. 9%), nervousness (7% vs. 2%)

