d. Early stopping rules.

Participants may be removed from the study under the following circumstances:

- Participant requests to withdraw from the study
- Participant requests that she have the ENG implant removed prior to conclusion of the study. (Of note, removal would be performed by the subject's clinician and not performed as part of the study.)
- Participant judged by the investigator to be at significant risk of failing to comply with the provisions of the protocol as to cause harm to self or seriously interfere with the validity of the study results.
- Participant takes emergency contraception during the study

8. Risks

a. Medical risks, listing all procedures, their major and minor risks and expected frequency.

The medical risks related to participation in this study fall into two categories: medication side effects or adverse reactions, and possible contraceptive failure.

Medication Adverse Reactions:

The most common adverse reactions for EFV are:

- Psychiatric symptoms – severe depression (2.4%), suicidal ideation (0.7%), nonfatal suicide attempts (0.5%), aggressive behavior (0.4%), paranoid reactions (0.4%), and manic reactions (0.2%)
- Central nervous system symptoms (overall incidence 53%) – dizziness (28.1%), insomnia (16.3%), impaired concentration (8.3%), somnolence (7%), abnormal dreams (6.2%), and hallucinations (1.2%) (usually begin during the first 2 days of therapy and resolve after 2-4 weeks).
- Rash (26%) – usually mild to moderate maculopapular skin eruptions that occur within the first 2 weeks of initiating therapy and typically resolve within 1 month

Additional adverse reactions to EFV include elevated liver enzymes, convulsions, elevated total cholesterol and triglycerides, and fat redistribution. Adverse reactions attributed to EFV occurred less frequently with the 400 mg daily dose compared to 600 mg[27].

It is possible that any changes in ENG concentrations that occur during and after the course of EFV could lead to increased incidence of adverse reactions to ENG. The most common adverse reactions leading to discontinuation of Nexplanon®/Implanon® are[7]**Error! Bookmark not defined.**:

- Bleeding irregularities (11.1%)
- Emotional lability (2.3%)
- Weight increase (2.3%)
- Headache (1.6%)
- Acne (1.3%)
- Depression (1.0%)

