Given that co-administration of EFV with the ENG implant may lead to decreased serum concentrations of ENG, participants may experience greater or lesser breakthrough bleeding than is typical with the ENG implant. They could also experience an improvement in progestin-related side effects with lower ENG concentrations.

Unintended Pregnancy

Since the goal of the study is to determine whether reduced-dose EFV lowers the serum concentration of ENG to a level where ovulation might occur, there is the possibility that a participant could ovulate during

Date: January 5th, 2017

Principal Investigator: [name], MPH

Application Number: NA_00087585

or after taking reduced-dose efavirenz. If she is sexually active during the study, this would put her at risk of an unintended pregnancy. There is also some concern that EFV may cause neural tube defects when taken during the first trimester. This risk was suggested by isolated case reports; however, larger reviews have found no increased risk in congenital anomalies with EFV.

b. Steps taken to minimize the risks.

Participants will be advised to take EFV at bedtime and on an empty stomach in an effort to minimize the central nervous system effects. They will also be counseled about the potential for psychiatric effects and rash as part of the informed consent process, and will be provided with contact information for study personnel should they experience any concerning symptoms. If needed, depending on the nature of the psychiatric symptoms or effects, participants will be referred for appropriate clinical care. This may include the emergency department, a psychologist, or the participant's primary care physician.

Participants will also be encouraged to either abstain from intercourse during the study period, or to use an additional backup method such as male or female condoms. They will be counseled about the potential for unintended pregnancy and teratogenic effects as part of the informed consent process. Participants will also be counseled about the availability of emergency contraception (either over-the-counter or by prescription) if they ever feel at risk for unintended pregnancy during the study (i.e. in the event of condom breakage).

c. Plan for reporting unanticipated problems or study deviations.

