Determining whether this highly-effective reversible contraceptive method is a safe and viable option for HIV-infected women on HAART will broaden these patients' contraceptive options, particularly when they wish to avoid pregnancy for an extended period of time. The knowledge gained from this study will also help determine whether the lifespan of Nexplanon®/Implanon® is reduced in women taking reduced-dose efavirenz. After Nexplanon®/Implanon® is inserted, there is an initial burst release of etonogestrel, and peak serum concentration is reached at a mean of 4 days after placement[7]. Serum ENG concentrations decline slowly over the three-year lifespan of the implant, and this study will provide information as to whether ENG concentrations remain sufficient to reliably suppress ovulation when EFV is taken simultaneously. If reduced-dose EFV causes ENG concentrations to decrease below the ovulation suppression threshold, the ENG implant may need to be replaced prior to the licensed three years.

10. Payment and Remuneration

- a. Detail compensation for participants including possible total compensation, proposed bonus, and any proposed reductions or penalties for not completing the protocol.

Participants will be compensated as follows:

- Screening visit = \$75
- Enrollment visit = \$45
- Follow-up visits (total of 12) = \$60 each = \$720 total
- Bonus payment for completion of study = \$180
- Parking/Bus tokens (total of 14) = \$5 each = \$70 total

This comes to a total of \$1090 for each participant at the end of the study. The bonus payment at the completion of the study will be made if there have been no significant deviations from the study protocol. Participants will not be compensated for visits that are not completed, and they will not receive the bonus if they are missing data for three or more visits.

11. Costs

- a. Detail costs of study procedure(s) or drug (s) or substance(s) to participants and identify who will pay for them.

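### Section 4f ends all study observation at pregnancy or a serious adverse event, so a woman with a serious event loses her remaining visits and the only planned post-efavirenz safety labs

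*Combined protocol and SAP*

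**What the plan says.** Section 4f is mandatory: "A participant will be removed from the study under the following circumstances". Its list has four entries: more than three missed visits, "She becomes pregnant", "She experiences a serious adverse event", and the woman's own request to stop. It does not say whether removal means stopping EFV, ending visits, or both.

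Section 4g, on premature exit, says that her ordinary medical care is unaffected. It describes no exit visit or exit tests. Section 8b provides for clinical referral for psychiatric symptoms, and 8c covers the reporting of deviations. Neither describes study follow-up of an adverse event.

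Section 7d gives a second list, under permissive wording (participants may be removed). It omits pregnancy and serious adverse events and adds other grounds, among them "Participant takes emergency contraception during the study".

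EFV is taken for 14 days and visits run to Day 42. Section 4a gives the reason for the later visits: "Continued monitoring for several weeks after cessation of EFV will allow us to follow subjects for the equivalent of a normal menstrual cycle". The stated aim is to learn whether ovulation suppression or mucus quality changed. Table 1 places safety labs and the urine pregnancy test at screening and again only in the last column, Day 42. Section 4a allows further pregnancy tests as needed.

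**The concern.** After Day 14 there is no dosing left to stop. Removal from then on ends only observation, and the later visits exist to observe what EFV did.

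For a serious adverse event this matters in two ways. The remaining ENG, hormone, ultrasound and mucus measurements are not taken. The Day 42 safety labs, the only ones planned after exposure, are also lost, although section 6 warns that EFV can raise liver enzymes even in people without liver disease. These are healthy volunteers taking EFV off-label, so a woman with a serious event is the one whose labs a reader would most want to see.

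Pregnancies on an implant taken with EFV are part of the rationale in sections 3 and 6. Yet section 7b has no place to report one, and its only stated consequence in the plan is removal.

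**Working it through.** **Inputs.** From Table 1, visits after study entry are on Days 2, 7, 11, 14 (during EFV) and 18, 21, 25, 28, 32, 35, 39, 42 (after EFV). EFV lasts 14 days (section 4a). Follow-up visits number 12 (section 10) and total visits 14 (sections 4a and 4b).

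**Reproducing the plan's count.** Screening + entry + follow-up = 1 + 1 + 12 = 14, which agrees with the stated total.

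**Share of follow-up after EFV.** Visits: 8/12 = 67%. Days: (42 − 14)/42 = 28/42 = 67%.

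**Visits lost by day of removal**, counting that day's visit as completed:

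| Removed at | Visits lost | Of these, after EFV | Day 42 labs lost |
|---|---|---|---|
| Day 2 | 11 | 8 (73%) | yes |
| Day 7 | 10 | 8 (80%) | yes |
| Day 11 | 9 | 8 (89%) | yes |
| Day 14 | 8 | 8 (100%) | yes |
| Day 28 | 4 | 4 (100%) | yes |
| Day 39 | 1 | 1 (100%) | yes |
| Day 42 | 0 | – | no |

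Most of the lost visits fall after EFV whenever removal happens, and any removal before Day 42 loses the closing labs.

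**Could the existing visits have shown recovery?** Section 8a says that nervous-system effects usually begin in the first 2 days and resolve in 2 to 4 weeks. From Day 2, four weeks runs to Day 2 + 28 = Day 30. It also says that rash appears within 2 weeks and typically resolves within 1 month. Taking a month as 30 days, a rash starting on Day 7 would run to about Day 37. Both fall inside the present schedule. These are typical courses, not courses of serious events.

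**Pregnancy.** A pregnancy found at the scheduled Day 42 test loses 0 visits. One found earlier by an as-needed test loses the visits after that day. EFV starts on the evening of Day 1, and a failure due to EFV needs ovulation, conception and then a positive test, so very early detection is unlikely.

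**Primary outcome and threshold rule.** The primary outcome (7a) is ENG before and after two weeks of EFV. Removal before Day 14 loses the end-of-EFV sample. Removal at or after Day 14 does not. The threshold rule (7c) counts women whose ENG falls below the ovulation-suppression level (90 pg/mL). Such a fall triggers no removal, and neither does ovulation.

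**How often?** The plan gives no combined rate of serious events. Its rate for grade 4 rash is 0.1%, so 18 × 0.001 = 0.018 expected cases. For nonfatal suicide attempts it is 0.5%, so 18 × 0.005 = 0.09. Assume, for illustration only, that each woman has probability p of either trigger:

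| p | At least 1 of 18: 1 − (1 − p)^18 | At least 4 of 18 (fewer than 15 left) |
|---|---|---|
| 2% | 30% | 0.04% |
| 5% | 60% | 1.1% |
| 10% | 85% | 9.8% |

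Over this range these triggers alone seldom take the sample below the planned 15, but one affected woman is quite possible.

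**The two lists side by side.** Section 4f is mandatory and 7d is discretionary. The only ground on both is the woman's own request, which is binding in one and optional in the other. Pregnancy and serious adverse events appear only in 4f, and emergency contraception only in 7d.

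**The case against.** The best defence is that little analysable information is lost. ENG, hormones, ultrasound and mucus are measured about twice a week, and ovulation comes before a detectable pregnancy, so the informative samples would usually be in hand. Nothing says that data from removed women are discarded. Events will be few in 18 healthy women who must use back-up contraception or abstain. No sentence forbids safety follow-up after removal, and the consent form is not among the documents. All of this stands. It limits the point for pregnancy and for the primary analysis, but it does not supply the missing exit labs or the cancelled visits after a serious event.

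Three stronger readings are tempting, and the documents support none of them.

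- A reader might infer that the women who remain are selected for having had no contraceptive failure, which would tilt the result towards maintained effect. But ovulation, a dominant follicle, favourable mucus and ENG below 90 pg/mL trigger no removal, and no passage restricts the analysis to completers.
- A reader might set a single pregnancy among 18 women against the implant failure rate quoted in section 6. That rate has no stated time base, and these women are followed for six weeks with back-up contraception.
- A reader might infer that lost visit payments discourage reporting of events or of emergency contraception. Section 10 pays every woman by completed visit, removal for emergency contraception is discretionary, and nothing in the plan shows such an effect.

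**Conclusion.** The point holds in a limited form. As written, 4f ends observation at a serious adverse event or pregnancy, at a cost of up to 11 of 12 follow-up visits after Day 2 and 8 of 12 at Day 14. Any exit before Day 42 also loses the only planned post-EFV safety labs. The loss falls mainly on serious adverse events; for pregnancy it is probably small. The primary ENG comparison suffers only if removal precedes Day 14, and the effect on the threshold rule is small. A direction of bias can be imagined, but its size cannot be derived from the documents.

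This rests on two assumptions: that removal from the study means no further study visits, which is the plain sense of 4f given the silence elsewhere, and that the last column of Table 1 is Day 42. The mismatch between 4f and 7d needs neither assumption.

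**What to change.** 1. Reword 4f so that pregnancy or a serious adverse event does not by itself end observation. A woman who consents keeps the already scheduled assessments that remain feasible.
2. Add to 4g that anyone leaving early has the Day 42 safety labs and pregnancy test at her last visit.
3. State in section 7 that any pregnancy and any serious adverse event will be reported descriptively, and that samples taken after such an event, or after emergency contraception, will be flagged in the analysis.
4. Reconcile 4f with 7d into one list, stating for each ground whether it is mandatory or discretionary and whether it ends EFV, observation or both.

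Whether and when EFV is stopped, and the clinical care of the event, remain for the investigator to define.

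The cost is a wording amendment. The visits are already planned. The downside is a few exit tests brought forward and some flagged samples.

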This will be a prospective, single arm pilot pharmacokinetic (PK) study. We will recruit 18 healthy, HIV-negative women aged 18 to 40 years who are using Nexplanon®/Implanon® for contraception and who are willing to take a reduced dose of EFV for 2 weeks. We will limit enrollment to women who have had the ENG implant in place 12 to 24 months to avoid the initial burst release of ENG after implant placement, and to target the time frame of concern based on case studies of contraceptive failures among women on HAART. Performing the study in women without HIV infection will allow us to evaluate any interactions between ENG and EFV without having to contend with the effects of other drugs that make up typical HAART regimens. A two-week course of EFV will be sufficient for EFV to reach steady-state concentration while minimizing exposure in these healthy volunteers. By using the reduced dose of EFV (400 mg daily instead of the standard 600 mg daily dose)

Over 6 weeks from study entry, we will perform twice-weekly (see visit schedule) quantitative assessments of serum ENG as well as serum hormone concentration analysis, pelvic ultrasound for markers of ovulation, and cervical mucus testing, as described below. Given the slow apparent clearance of ENG and based on previous PK studies, we estimate that sparse sampling will be adequate to assess changes in ENG clearance during EFV administration. EFV will be administered for 14 days from the beginning of the study, after collection of baseline samples for ENG concentration determination. All study procedures will take place at the Johns Hopkins Bayview Medical Center's Clinical Research Unit (CRU). All blood tests will be performed locally except for ENG concentrations, which will be performed at Columbia University

Date: January 5th, 2017

Principal Investigator: [name], MPH

Application Number: NA_00087585

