in New York City. ENG samples will be collected, frozen, and batch-shipped. The subject population will be healthy, HIV-negative women using Nexplanon®/Implanon®, with the anticipation that the findings will be applicable to HIV-infected women. There is limited data regarding the use of the etonogestrel implant in obese women. While two small studies found lower etonogestrel concentrations in obese women than normal weight women, the differences were not statistically significant[16, 17]. Overweight and obese women using the etonogestrel implant do not experience contraceptive failures more frequently than overweight or obese women using an intrauterine device[18]. We will limit enrollment to women with a BMI <30 kg/m² so as to limit any effect morbid obesity may have on etonogestrel concentrations. We expect that the study will take a total of 12 months to complete. A screening visit to confirm eligibility will occur prior to initiation of study visits.

Screening: Potential subjects will be identified by their treating providers as meeting basic eligibility criteria (appropriate age and currently using Nexplanon®/Implanon®). Each candidate will be informed of the study purpose and design, and will be given contact information for study personnel if she is interested in enrolling. With her permission, the potential subject's contact information will also be forwarded to study personnel, who will then contact her by phone. During a phone interview, details of the study will be discussed with her, after which she will be asked to come to the Bayview CRU for an in-person interview. During this visit, she will be asked to read and sign the approved consent form, undergo a history and physical exam, and have baseline laboratory tests performed (hematologic and metabolic panels as described in Inclusion Criteria, serum HIV, urine pregnancy test), as well as a baseline ultrasound to ensure her ovaries are detectable. Study personnel will review the results of the laboratory tests, and if all results are in the specified ranges, the subject will be contacted to schedule the start of the study protocol.

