Data collection: After successful screening, women will be asked to take 14 days of EFV in a once-nightly 400 mg regimen. We will collect blood samples for baseline ENG concentration on the day participants begin taking EFV, before the first dose (Day 1, times 0 hour, 1 hour, and 2 hours). The first dose of EFV will be taken in the evening of Day 1, and the next blood sample for ENG concentration will be drawn twelve to twenty hours after the first dose of EFV. (For example, if a participant takes her first dose of EFV at 10 PM on Day 1, she will be asked to return to the CRU between 10 AM and 6 PM on Day 2.) We will then obtain subsequent samples every 3 to 4 days (+/- 1 day) for the remainder of the two week EFV course and for 4 additional weeks (through Week 6 of study participation). This is a total of 14 outpatient visits, including screening. All serum samples will be analyzed for concentrations of ENG, which will be used to derive the ENG area under the concentration-time curve (AUC), the maximum and minimum observed serum drug concentration (C_{max}, C_{min}), and the apparent average serum concentration at steady-state (C_{ss,avg}) using WinNonlin®. EFV concentrations will be determined from plasma samples obtained at 2 timepoints during EFV administration, and measured using a validated LC/MS/MS assay in the Clinical Pharmacology Analytical Laboratory of the Johns Hopkins Hospital.

Table 1: Participant Visit Schedule and Timing of Study Assessments

Visit	Screening	Study Entry			Week 1		Week 2		Week 3		Week 4		Week 5		Week 6	
		1			2	7	11	14	18	21	25	28	32	35	39	42
Serum Tests		0 hr	1 hr	2 hr												
ENG		X	X	X	X	X	X	X	X	X	X	X	X	X	X	X
EFV					X			X								
FSH		X			X	X	X	X	X	X	X	X	X	X	X	X
LH		X			X	X	X	X	X	X	X	X	X	X	X	X
Estradiol		X			X	X	X	X	X	X	X	X	X	X	X	X
Progesterone		X			X	X	X	X	X	X	X	X	X	X	X	X
Safety Labs	X															X
UPT	X															X
HIV	X															X
TVUS	X				X	X	X	X	X	X	X	X	X	X	X	X
CM	X				X	X	X	X	X	X	X	X	X	X	X	X

Date: January 5th, 2017

Principal Investigator: [name], MPH

Application Number: NA_00087585

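### Eligibility requires a negative pregnancy test at study entry, but the visit schedule has none on Day 1 before the first efavirenz dose

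*Combined protocol and SAP*

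**What the plan says.** The inclusion criteria in Section 5 include "Negative urine hCG pregnancy test at study entry", with no look-back window. The laboratory criterion in the same list does have one: "Normal laboratory values within 30 days of study entry, as specified below". The HIV criterion also allows 30 days, counted from enrollment.

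Section 4a shows what study entry means. The design text says "Over 6 weeks from study entry, we will perform twice-weekly" assessments will be made, so the six weeks start there. The table titled "Table 1: Participant Visit Schedule and Timing of Study Assessments" heads Day 1 (0, 1 and 2 hours) as Study Entry and gives Screening its own column. Its urine pregnancy test row is marked at Screening and at Day 42 only.

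The Screening paragraph of Section 4a agrees with the table. The baseline tests at that visit are listed as "hematologic and metabolic panels as described in Inclusion Criteria, serum HIV, urine pregnancy test". Once the results have been reviewed and found acceptable, "the subject will be contacted to schedule the start of the study protocol". The Data collection paragraph describes baseline etonogestrel samples on Day 1 and the first efavirenz dose that evening, and mentions no pregnancy test. Later in Section 4a, repeat urine tests are allowed at any time if needed, but none is tied to Day 1.

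**The concern.** Two rules in the same protocol disagree. The eligibility rule asks for a negative result at study entry, and the schedule that staff will work from does not include the test at that visit. A site following Table 1 would give efavirenz without the required test, and each such participant would be an eligibility deviation. A pregnancy that began between screening and Day 1 could also go undetected until after dosing had started.

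The protocol's own account of the drug is what gives this weight. Efavirenz is used off-label here in women with no therapeutic need for it. Section 6 raises a neural-tube concern for exposure in the first 5 to 6 weeks of pregnancy, and a test done some weeks before Day 1 could have preceded conception. Section 8a tempers this by noting that larger reviews found no excess of congenital anomalies. Pregnancy is also a reason for removal under Section 4f. This is a matter of participant safety and of consistency within the protocol. It has no bearing on the sample size or on the etonogestrel analysis.

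**Working it through.** The plan gives no figure to reproduce, so the check is a reading of Table 1 against the text, followed by simple date arithmetic.

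**1. Where the test is scheduled.** Table 1 has 17 columns: the row label, Screening, Day 1 at 0, 1 and 2 hours, and Days 2, 7, 11, 14, 18, 21, 25, 28, 32, 35, 39 and 42. Because the table was read from a PDF, the alignment was checked on other rows:
- Etonogestrel falls on Day 1 at 0, 1 and 2 hours and on every later day, as the text describes.
- Efavirenz falls on Days 2 and 14, which gives the two time points stated in the text.
- Visits: 1 screening + 1 (Day 1) + 12 follow-up = 14, as stated in Section 4b.

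On the same alignment the pregnancy test row is marked at Screening and Day 42, which is 2 of 14 visits. On Day 1 it is marked 0 times.

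**2. Whether study entry could mean screening.** The laboratory criterion allows values from up to 30 days before study entry, and the Screening paragraph says those laboratory tests are done at the screening visit. That look-back makes sense only if study entry comes after screening. The Table 1 column heading and the six-week count point the same way.

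**3. Timing.** Inputs are nominal days from Table 1: entry and first dose on Day 1, end of the 14-day course on Day 14, next scheduled test on Day 42. The protocol states no window for the pregnancy test. The 30-day laboratory window is *assumed* for it because both are done at the screening visit.

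| Quantity | Calculation | Days |
|---|---|---|
| Maximum age of the screening test at Day 1 (assumed) | laboratory window | 30 |
| Day 1 to next scheduled test | 42 − 1 | 41 |
| Maximum gap between scheduled tests (assumed) | 30 + 41 | 71 |
| End of efavirenz course to next scheduled test | 42 − 14 | 28 |

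Only the first and third rows rest on the assumption. If screening were done just before Day 1, the first row would shrink towards zero and the third towards 41. The whole efavirenz course lies between the two scheduled tests in either case.

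**4. Expected pregnancies.** No estimate is given. Section 6 quotes an implant failure rate below 0.05% without a time period, and every woman has already tested negative at screening. The documents therefore do not support a numerical bound at Day 1.

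**The case against.** The strongest reply is that the safeguard already exists. The criterion binds whatever Table 1 shows, so a woman without a negative test at entry is ineligible, and the provision for repeat tests lets staff do one on Day 1 without an amendment. On this view the defect is one empty table cell. That is fair as to size. But a discretionary repeat does not guarantee an eligibility test, and nothing in the schedule prompts staff to do it.

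A second reply is that the authors meant the screening test to satisfy the criterion. The screening visit exists to confirm eligibility, and the protocol uses its timing terms loosely: Section 4b counts screening among the visits made during the six weeks. This reading is possible, but it conflicts with the Table 1 heading and with the 30-day window in the same list. If it is what was meant, the criterion is misworded and lacks a maximum interval, so a correction is still needed.

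Third, the 41 days after Day 1 would remain after the fix, and the efavirenz course would still fall between two scheduled tests. That is correct. The fix removes only the pre-dose interval, whose length the protocol does not state.

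Fourth, other protections lower the risk, and they stand. Each woman must "Agree to use an additional reliable method of contraception while participating in the study", with abstinence among the accepted options. Screening includes an ultrasound, although its stated purpose is "as well as a baseline ultrasound to ensure her ovaries are detectable". Ovarian hormones are measured on Day 1 and at every later visit, and ultrasound is repeated from Day 2. None of these is a pregnancy test before dosing, and Table 1 shows no ultrasound on Day 1.

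**Conclusion.** The concern holds, as a minor point. The criterion and the schedule conflict, and the schedule as written provides no pregnancy test on Day 1 before the first efavirenz dose for any of the 18 women. The conclusion rests on reading study entry as Day 1, which Table 1 and the neighbouring laboratory criterion both support. The 30-day and 71-day figures rest on the further assumption that the laboratory window applies to the pregnancy test; the conflict itself does not depend on them. The absolute risk is small and the primary endpoint is not affected. The correction is worth making because it costs almost nothing and protects healthy volunteers.

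**What to change.** Mark a urine pregnancy test in Table 1 at Day 1, at the 0-hour time point, and add a sentence to the Data collection paragraph stating that a negative result is required before efavirenz is dispensed or taken. The criterion in Section 5 can then stay as it is. The cost is 18 urine tests (one per woman × 18 women), one table entry and one sentence. Each woman already attends on Day 1 for samples at 0, 1 and 2 hours, so no extra visit or staff are needed.
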